4.2. Participant Dispositions

The number and percentage of patients randomized and treated in the study and patients included in each analysis set will be presented, together with the number and percentage of patients who withdrew from the study prematurely and a breakdown of the corresponding reasons for withdrawal for both double-blind treatment period and period 2. The subject completion status and discontinuation reasons in both double-blind treatment period and period 2 will be listed.

The number and percentages of screen failure and corresponding reasons will be summarized. The subjects with screen failure reasons will also be listed.

4.3. Primary Endpoint/Estimand Analysis

4.3.1. Definition of endpoint

The primary endpoint is Change from Baseline of DAS28-CRP at Week 12.

4.3.2. Main analytical approach

Observed values at baseline and changes from baseline to Week 12 endpoint in DAS28-CRP will be summarized by treatment arm and provided as listing.

A restricted maximum likelihood based, MMRM analysis will be used to analyze the primary endpoint. The MMRM model will include treatment, strata (previous RA therapy population), baseline value, visit, treatment-by-visit interaction in the model as fixed factors, and patient as a random factor. An unstructured covariance matrix will be used to model the within-subject errors. If this analysis fails to converge, other structures will be tested (in this order: Toeplitz, Autoregressive with heterogeneity, and Compound Symmetry). The Kenward-Roger approximation will be used to estimate denominator degrees of freedom. Significance tests will be based on least squares means and Type III tests. The data on or after the treatment discontinuation will not be included in MMRM analysis.

For participants who discontinue study intervention and/or receive rescue therapy, post-discontinuation or post-rescue observations will not be included.

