9.4. Statistical Analyses

9.4.1. General Considerations

Statistical analysis of this study will be the responsibility of sponsor or its designee. The independent variable, previous RA therapy population, is defined as only csDMARD experienced or bDMARD/tsDMARD experienced participants. Unless otherwise indicated in the statistical analysis plan (SAP), the analyses will be conducted as follows:

Analysis for	Description
Primary and secondary endpoint analyses comparing LY3462817 to placebo	Tested at a 2-sided α level of 0.05 for frequentist analyses.
Adjustments for multiplicity	None to be performed since this a proof of concept Phase 2 study.
Baseline	Defined as the last available value before the first dose of study intervention for both efficacy and safety analyses. In most cases, this value will be what is recorded at the randomization visit (Visit 2).
Change from baseline	Will be calculated as the visit value of interest minus the baseline value.
Efficacy and patient-reported outcome (PRO) analysis	
Analysis models may contain the independent variables such as treatment group, baseline disease activity, and previous RA therapy population.
 
Endpoint analyses will use the mITT population unless otherwise specified.

Dichotomous responder endpoints	
Missing data will be imputed using the nonresponder imputation (NRI) method.
 
Will be analyzed using a logistic regression model with treatment group, baseline disease activity, and previous RA therapy population as model covariates.

NRI analysis	
Participants will be considered nonresponders if:
 
 they do not meet all the clinical response criteria they are noncompliant with concomitant medication rules (Section 6.5) they permanently discontinue study intervention at any time before the end of the treatment period for any reason, or they are randomized and do not have at least 1 postbaseline observation.
Continuous efficacy endpoints	
Mixed-effects model for repeated measures (MMRM) will be used.
 
The MMRM model will include treatment, strata (previous RA therapy population), baseline value, visit, treatment-by-visit interaction in the model as fixed factors, and patient as a random factor.
 
An unstructured covariance matrix will be used to model the within-subject errors. If this analysis fails to converge, other structures will be tested (in this order: Toeplitz, Autoregressive with

Analysis for	Description

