1.2. Study Design

This is a Phase 2, proof-of-concept, placebo-controlled, double-blind, randomized study in adult participants with moderately to severely active RA who have had an inadequate response to csDMARDs, or to bDMARDs/tsDMARDs. Participants will be administered LY3462817 or placebo IV Q4W.

Screening Period (Visit 1, Days -42 to -1)

Participants will sign the informed consent document(s) at Visit 1, prior to completion of any procedures. Participants will be evaluated for study eligibility ≤ 42 days prior to the baseline visit (Visit 2).

Period 1: Double-blind Treatment (Visits 2 to 6; 12 weeks)

At the baseline visit (Visit 2), participants who fulfill the eligibility criteria will be randomized to receive LY3462817 700 mg, LY3462817 300 mg, or placebo in an allocation ratio of 2:1:1. The double-blind treatment period will establish the clinical efficacy and safety of LY3462817. The study will be evaluated for the primary objective at the end of the double-blind treatment period.

Period 2 (Visits 6 to 10; 12 weeks)

In Period 2, all subjects will receive LY3462817 to assess safety and tolerability data and explore clinical activity with additional dosing. At Week 14, participants will be evaluated for clinical benefit.

Posttreatment Safety Follow-up Period (Visits V801 and 802; 12 weeks)

Following Period 2, participants will be followed posttreatment for 12 weeks to assess safety, study drug exposure, and clinical disease activity measures.

2. Statistical Hypotheses

For the primary estimand with primary endpoint, change from baseline to week 12 in DAS28-CRP, the following 2 (confirmatory) 1-sided hypotheses are planned to be tested for LY3462817 700 mg versus placebo. Let the mean treatment difference be defined as $\mu = (\text{LY3462817 700 mg} - \text{placebo})$.

$H_0: \mu \geq 0.0$ against $H_a: \mu < 0.0$

Operationally the hypotheses will be evaluated by 2-sided tests.

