4.1. General Considerations

The independent variable, previous RA therapy population, is defined as only csDMARD experienced or bDMARD/tsDMARD experienced participants. Unless otherwise indicated in the statistical analysis plan (SAP), the analyses will be conducted as follows:

Analysis for	Description
Primary and secondary endpoint analyses comparing LY3462817 to placebo	Tested at a 2-sided level of 0.05 for frequentist analyses
Adjustments for multiplicity	None to be performed
Baseline	Defined as the last available value before the first dose of study intervention for both efficacy and safety analyses. In most cases, this value will be what is recorded at the randomization visit (Visit 2).
Change from baseline	Will be calculated as the visit value of interest minus the baseline value.
Efficacy and patient-reported outcome (PRO) analysis	Analysis models may contain the independent variables such as treatment group, baseline disease activity, and previous RA therapy population. Endpoint analyses will use the FAS unless otherwise specified.
Dichotomous responder endpoints	Missing data will be imputed using the nonresponder imputation (NRI) method. Will be analyzed using a logistic regression model with treatment group, baseline disease activity, and previous RA therapy population as model covariates.
NRI analysis	Participants will be considered nonresponders if: 
 • they do not meet all the clinical response criteria • they are noncompliant with concomitant medication rules

	
 • they permanently discontinue study intervention at any time before the end of the treatment period for any reason, or • they are randomized and do not have at least 1 postbaseline observation.
Continuous efficacy endpoints	
Mixed-effects model for repeated measures (MMRM) will be used.
 
The MMRM model will include treatment, strata (previous RA therapy population), baseline value, visit, treatment-by-visit interaction in the model as fixed factors, and patient as a random factor.
 
An unstructured covariance matrix will be used to model the within-subject errors. If this analysis fails to converge, other structures will be tested (in this order: Toeplitz, Autoregressive with heterogeneity, and compound symmetry.).
 
The Kenward-Roger approximation will be used to estimate denominator degrees of freedom. Significance tests will be based on least squares means and Type III tests.

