4.9. Changes to Protocol-Planned Analyses

There is no change to protocol-planned analyses.

5. Sample Size Determination

Approximately 80 participants will be randomly assigned to study intervention. At the completion of the study, approximately 40 participants will have been randomized to LY3462817 700 mg and 20 participants will have been randomized to LY3462817 300 mg and placebo during the double-blind treatment. All randomized participants in FAS will be considered evaluable.

Assuming -1.80 and -0.75 as the DAS28-CRP change from baseline for LY3462817 700 mg and placebo, respectively, with standard deviation equal to 1.25, a 2-sided t-test with alpha = 0.05 has greater than 80% power to detect a statistically-significant difference in DAS28-CRP change from baseline at Week 12.

6. Supporting Documentation

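### If the unstructured MMRM fails, the first fallback reads as an equal-variance Toeplitz matrix, which understates the Week 12 standard error if variance rises over visits

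*SAP*

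**What the plan says.** Protocol 9.4.1 sets the starting point for continuous endpoints: "An unstructured covariance matrix will be used to model the within-subject errors". SAP 4.1 and 4.3.2 repeat it. For non-convergence, SAP 4.3.2 gives the order: "If this analysis fails to converge, other structures will be tested (in this order: Toeplitz, Autoregressive with heterogeneity, and Compound Symmetry". SAP 4.1 and the subgroup models in SAP 4.7.2 carry the same list. Protocol 9.4.1 begins the same way but leaves the list open after the autoregressive structure.

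The same sections add a random patient effect to the model and name Kenward-Roger for the denominator degrees of freedom. No robust (sandwich) standard error is named. SAP 4.3.3 and 4.3.4 rule out sensitivity and supplementary analyses of the primary endpoint. SAP 4.8 applies the primary method at the interim as well.

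The only variability figure is in the sample-size text (protocol 9.2, SAP 5): a comparison "with standard deviation equal to 1.25" for the Week 12 change. No SD is given for Weeks 2, 4 or 8.

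**The concern.** The trial is decided by one contrast, 700 mg versus placebo at Week 12. An equal-variance structure replaces the Week 12 variance with, roughly, the average variance over the four post-baseline visits. If the earlier visits vary less than Week 12, that average is too small, and so are the standard error, the p-value and the interval width.

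Equal-variance Toeplitz stands first in the order, ahead of the one named structure that lets variances differ. Kenward-Roger adjusts small-sample inference within the fitted structure and does not repair a wrong variance pattern. With no robust standard error and no sensitivity analysis, nothing else in the plan would show the problem.

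**Working it through.** **Inputs from the documents.** Two-sided alpha 0.05; Week 12 SD 1.25; assumed changes of -1.80 and -0.75 (difference 1.05); about 40, 20 and 20 participants on 700 mg, 300 mg and placebo (SAP 5). The protocol's schedule of activities has hsCRP, joint counts and patient global at Weeks 2, 4, 8 and 12, so the model has four repeated DAS28-CRP values.

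**Assumed.** The SDs at Weeks 2, 4 and 8; the within-patient correlations; 10% missing-at-random dropout in the full-model simulation.

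**Step 1: the plan's own figure.** The plan states that "a 2-sided t-test with alpha = 0.05 has greater than 80% power". The standard error of the difference is 1.25 × √(1/40 + 1/20) = 0.342. Then 1.05/0.342 = 3.07, and Φ(3.07 - 1.96) gives 86.6%. The noncentral t with 58 df gives 85.5%. The claim reproduces and is not affected by this point.

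**Step 2: closed form.** With treatment-by-visit in the model and near-complete data, the Week 12 standard error under equal-variance Toeplitz is about the true one times r = √(mean variance over four visits / Week 12 variance). Type I error is then about 2 × [1 - Φ(1.96 r)]. For the moderate pattern below, the mean variance is (0.81 + 1.1025 + 1.3225 + 1.5625)/4 = 1.199, r = √(1.199/1.5625) = 0.876, and 1.96 r = 1.717, which gives 8.6%.

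**Step 3: simulation under the null.** Two checks were run: the SAP's REML model with Kenward-Roger (3,000 trials per pattern), and a simpler complete-data REML fit (2,000 to 4,000 trials per pattern). Toeplitz was applied to every simulated trial, so the rates are those that apply when the fallback is used.

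| Pattern | SDs at Weeks 2/4/8/12 | r | Closed form | Full model | Complete data |
|---|---|---|---|---|---|
| Constant | 1.25 throughout | 1.000 | 5.0% | 4.8% | 4.6% |
| Mild growth | 1.10/1.15/1.20/1.25 | 0.941 | 6.5% | 6.7% | 6.6% |
| Moderate growth | 0.90/1.05/1.15/1.25 | 0.876 | 8.6% | 8.7% | 8.4% |
| Strong growth | 0.70/0.90/1.10/1.25 | 0.807 | 11.4% | not run | 11.4% |
| Falling | 1.40/1.35/1.30/1.25 | 1.061 | 3.8% | not run | 3.7% |

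The full model shows the mechanism. The mean estimated standard error was 0.334 against an empirical SD of 0.360 under mild growth, and 0.309 against 0.354 under moderate growth. Unstructured covariance stayed at 4.5% to 5.2% under every growing pattern. Compound symmetry behaved like Toeplitz (7.0% mild, 8.6% moderate).

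**Step 4: effect on the whole trial.** Overall type I error is about (1 - f) × 5% + f × (rate given fallback), where f is the chance of fallback, taken as unrelated to the test result. The documents do not give f. With f = 1% and the moderate pattern: 0.99 × 5 + 0.01 × 8.6 = 5.04%. With f = 5%: 0.95 × 5 + 0.05 × 8.6 = 5.18%, and 5.32% for the strong pattern.

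**Step 5: the alternative.** Heterogeneous Toeplitz gave 4.7% when the true correlation was Toeplitz in form, and 3.7% to 4.4% under growing SDs when correlation decayed with actual weeks. The slight conservatism arises because the visits are unequally spaced. With four visits it needs 4 variances + 3 correlations = 7 parameters, against 1 + 3 = 4 for the equal-variance form and 10 for unstructured.

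**The case against.** The strongest objection is that the plan would seldom use Toeplitz. With about 80 participants, four visits and ten covariance parameters, an unstructured fit usually converges. A reader might take 6.5% to 11.4% as the type I error of this trial's primary test; the documents do not support that, and Step 4 shows a much smaller overall effect. This stands.

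A reader might also infer that DAS28-CRP variance is known to grow here. The documents give one SD, at one visit. Constant variance gives no inflation and falling variance gives a conservative test, so the condition on rising variance cannot be dropped. This stands too.

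Third, that Toeplitz means the equal-variance form is an inference from the wording, not a statement in the SAP. Even so, a text that qualifies one structure and not its neighbours should say which form it means.

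Fourth, this is a proof-of-concept study without multiplicity adjustment, and posterior probabilities also inform development decisions (protocol 9.5, SAP 4.8). That lowers the stakes but does not make the fallback a good choice.

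The objection is weakest on the random patient effect. Fitted literally beside an unstructured residual matrix, it is not separately identifiable, which makes a convergence failure, and so the fallback, more likely. Under Toeplitz it leaves the visit variances equal and repairs nothing. The interim also has fewer data: 40% to 60% of 80 is 32 to 48 participants.

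**Conclusion.** The point holds as a conditional one. If the unstructured fit fails, if Toeplitz is meant in its equal-variance form, and if residual variance rises toward Week 12, the primary test exceeds its nominal 5%: about 6.5% with mild growth and 11.4% with strong growth, with standard errors about 6% to 19% too small. These sizes rest on assumed earlier-visit SDs, with Week 12 fixed at 1.25. If any of the three conditions fails, this mechanism gives no inflation. Because fallback should be uncommon, the effect on overall type I error is small. The change is worth making because it is cheap and because choosing a covariance structure after unblinding would be post hoc.

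**What to change.** Before any unblinding, including the interim:

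- In SAP 4.1, 4.3.2 and 4.7.2, make the fallback order heterogeneous Toeplitz, then heterogeneous autoregressive, then heterogeneous compound symmetry. Each keeps a separate Week 12 variance. Only the first was simulated here.
- Remove the random patient effect from the same sections and let the residual matrix carry the within-patient correlation.
- If any equal-variance structure is kept, specify a robust (sandwich) standard error with it.
- Align protocol 9.4.1. Alternatively, describe the change and its reason in the SAP and clinical study report, as protocol 9.4.1 allows for changes that do not affect a principal feature. In that case the SAP Introduction and SAP 4.9, which report no changes from the protocol, need updating.

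The cost is wording, three more variance parameters than equal-variance Toeplitz (7 against 4, still fewer than 10), and a slightly conservative test, about 3.7% to 4.4%, when correlation decays over the unequally spaced visits.

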Clinician-Administered Tender/Swollen Joint Count (TSJC) (68/66)	X	X	X	X	X	X	X	X	X	X	X	X	X	Collected via an electronic tablet device. These joint counts will be performed by the Joint Assessor (Section 6.3). Determine prior to dosing
Physician's Global Assessment of Disease Activity (PhGADA_VAS)	X	X	X	X	X	X	X	X	X	X	X	X	X	Determine prior to dosing
Clinician-Administered Assessments (Paper)														
C-SSRS Screening/Baseline	X													Administer before any clinical assessments and dosing
C-SSRS Since Last Assessed		X	X	X	X	X	X	X	X	X	X	X	X	Administer before any clinical assessments and dosing
Self-harm Supplement Form	X	X	X	X	X	X	X	X	X	X	X	X	X	
Self-Harm Follow-Up Form	X	X	X	X	X	X	X	X	X	X	X	X	X	
Laboratory Tests and Sample Collections														
Hematology	X	X		X	X	X	X	X	X	X	X	X	X	Collect prior to dosing
Clinical Chemistry	X	X		X	X	X	X	X	X	X	X	X	X	In addition to scheduled assessments, these laboratory tests may also be performed as clinically indicated. Collect prior to dosing.

Study J1A-MC-KDAD	Screen	Period 1: Double-blind treatment					Period 2				ED	Post-treatment follow-up		Comments
Day ± Visit Tolerance	-42 to -1	1	14 ± 7	28 ± 7	56 ± 7	84 ± 7	98 ± 7	112 ± 7	140 ± 7	168 ± 7	Any	196 ± 7	252 ± 7	Visit 1 procedures may be conducted over more than 1 day as long as all tasks are completed within the tolerance window.
Week	-	2	4	8	12	14	16	20	24	-	28	36 or ETV + 12		
Visit number	V1	V2	V3	V4	V5	V6	V7	V8	V9	V10	ET	V801	V802	
Procedures														
Urinalysis	X	X			X			X		X	X		X	In addition to scheduled assessments, these laboratory tests may also be performed as clinically indicated. Collect prior to dosing.
Serum pregnancy	X													For all women of childbearing potential (Section 10.4).
Urine pregnancy (local)		X		X	X	X		X	X	X	X	X	X	Determine results prior to dosing
Follicle Stimulating Hormone (FSH)	X													For women who are considered postmenopausal to confirm postmenopausal status.
C-Reactive Protein, high-sensitivity (hsCRP)	X	X	X	X	X	X	X	X	X	X	X	X	X	Collect prior to dosing
Erythrocyte sedimentation rate (ESR)	X	X				X				X	X	X	X	Collect prior to dosing
Rheumatoid factor (RF)	X	X				X				X	X	X	X	Collect prior to dosing
Anticyclic citrullinated peptide (anti-CCP)	X	X				X				X	X	X	X	Collect prior to dosing
Soluble PD-1		X	X	X	X	X		X		X	X	X	X	Collect prior to dosing
Soluble PD-L1		X	X	X	X	X		X		X	X	X	X	Collect prior to dosing.

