	
heterogeneity, etc.).
 
The Kenward-Roger approximation will be used to estimate denominator degrees of freedom.
 
Significance tests will be based on least squares means and Type III tests.

Participant Disposition	
A detailed description of participant disposition will be provided, including a summary of the number and percentage of participants entered into the study and randomized, and number and percentage of participants who complete the study or discontinue, both overall and by reason for discontinuation. A summary of important protocol deviations will be provided.

Participant Characteristics	
Demographic data are collected and responded to demonstrate that the study population represents the target patient population. A summary of baseline participant characteristics, historical diagnoses, preexisting conditions, and prior therapies will be reported by treatment group using descriptive statistics. Other participant characteristics will be summarized by treatment group as deemed appropriate.

Concomitant Therapy	
Previous and concomitant medications will be summarized by treatment group and will be presented by Anatomical Therapeutic Chemical drug classes using the latest version of the WHO drug dictionary.

Treatment Compliance	
No analyses are planned to assess treatment compliance, given that participants will receive study intervention directly from the investigator or designee at the study site, under medical supervision (Section 6.4).

Additional imputation methods may be considered for all endpoint types.

Estimands for Double-Blind Treatment Period

Endpoints	Estimand strategy	Estimand description	Use post-discontinuation data?	Imputation	Possible analysis method (estimator)
Primary endpoint and all other continuous efficacy and PRO endpoints	Hypothetical efficacy	Mean change from baseline (and mean scores) had all subjects remained on randomized treatment.	No, only use data up until discontinuation	Participants who discontinue study intervention have remaining data imputed* to reflect the expected outcome had the subject remained on the study treatment without using restricted medications** (assume missing at random [MAR])	MMRM model under MAR is applied to the data prior to treatment discontinuation

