2.1. Multiplicity Adjustment

This is a proof of concept study. No adjustments will be made to adjust the performed efficacy analysis for multiplicity.

3. Analysis Sets

The following analysis data sets are defined to estimate the estimands defined in the protocol and to address safety.

Analysis Data Sets	Description
Full Analysis Set (FAS) for the primary estimand and for the secondary estimand for the secondary objective	
• All participants randomly assigned to study intervention and who take at least 1 dose of study intervention. Participants will be included in the analyses according to the planned intervention• For participants who discontinue study intervention and/or receive rescue therapy, post-discontinuation or post-rescue observations will not be included.
Safety analysis set to be used for safety assessments	
• All participants who are exposed to study intervention. Participants will be included in the analyses according to the intervention they actually received.• All observed data will be included in the analysis set.
Pharmacokinetic(PK) analysis set to be used for PK assessments	
• All participants randomly assigned to study intervention and who take at least 1 dose of study intervention and have PK data available.• All observed data until discontinuation of intervention will be included in the analysis set.

4. Statistical Analyses

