The baseline period is defined as Visit 1 through pre-dose Visit 2. The Double-blind Treatment Period starts after the first injection of study treatment at Visit 2 (Week 0) and ends on the date of Visit 6 (Week 12) or the early discontinuation visit. The Period 2 starts after the date of Visit 6 (Week 12) or the early discontinuation visit and lasts up to 24 weeks following the last injection of study treatment. Additional follow-up beyond 24 weeks may be deemed necessary and, if so, any data collected will be considered as part of Period 2.

Unless otherwise specified, baseline for the Treatment Period is defined as the last non-missing assessment on or prior to the date of the first injection of study treatment, scheduled to be given at the end of Visit 2. Any assessment collected after the first injection through the date of the Week 12 or early discontinuation visit is defined as post-baseline for the Treatment Period.

Data collected at early discontinuation visits will be mapped to the next planned visit number for that patient. For by-visit summaries, only visits in which a measure was scheduled to be collected will be summarized.

Summaries of safety data collected during Period 2 will be presented separately. Unless otherwise specified, follow-up baseline is defined as the last non-missing assessment on or prior to the date of Week 12 or the date of the early discontinuation visit.

Change from baseline will be calculated as the post-baseline value minus the baseline value. Percent change from baseline is defined as $(100 \times (\text{post-baseline} - \text{baseline}) / \text{baseline})$. If all baseline values are missing for a particular variable, the change from baseline and percent change from baseline will not be calculated.

The statistical analyses of efficacy, health outcomes, and safety measures will be performed using SAS Version 9.4 or higher. Lilly will be responsible for conducting analyses.

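### The SAP does not say consistently whether DAS28-CRP values from the day treatment stops enter the primary MMRM; read literally, its most specific rule deletes valid on-treatment values

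*SAP*

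**What the plan says.** The rule for the primary model is in SAP 4.3.2: "The data on or after the treatment discontinuation will not be included in MMRM analysis". The closing sentence of the same section is narrower, saying that "post-discontinuation or post-rescue observations will not be included". The Full Analysis Set definition in SAP Section 3 uses that narrower wording: "For participants who discontinue study intervention and/or receive rescue therapy, post-discontinuation or post-rescue observations will not be included".

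SAP 4.1 adds two general rules. One sets the post-baseline window: "Any assessment collected after the first injection through the date of the Week 12 or early discontinuation visit is defined as post-baseline". The other assigns visits: "Data collected at early discontinuation visits will be mapped to the next planned visit number for that patient".

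The estimand table in Protocol 9.4.1 points both ways in one row. Under use of post-discontinuation data it says "No, only use data up until discontinuation". Under the estimator it says "MMRM model under MAR is applied to the data prior to treatment discontinuation".

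On timing, the Schedule of Activities (Protocol 1.3) says of joint counts: "These joint counts will be performed by the Joint Assessor (Section 6.3). Determine prior to dosing". Patient global and hsCRP are also taken before dosing. All three are scheduled at the early discontinuation visit, and Week 12 is itself a dosing visit. SAP 4.3.3 and 4.3.4 plan no sensitivity or supplementary analysis of the primary endpoint.

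**The concern.** Two programmers could each follow the SAP faithfully and build different primary datasets. The records at issue are few, but they can include the primary endpoint itself. A participant infused at Weeks 0, 4 and 8, assessed before dosing at Week 12, who then stops without the fourth infusion, has a Week 12 value reflecting 12 weeks of randomized treatment. That is the quantity the hypothetical estimand seeks, and 'on or after' removes it.

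The choice also bears on the missing-at-random assumption in Protocol 9.4.1. If a poor result at a visit prompts stopping, keeping that result lets the model account for the dropout. Deleting it makes the dropout depend on a value the model no longer sees.

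The same method serves the interim analysis (SAP 4.8), and Protocol 9.5 allows early termination for futility, so a shift toward no effect is not automatically harmless.

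**Working it through.** **1. Which records the wordings treat differently.** Take the participant above, whose last infusion was at Week 8.

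| Discontinuation dated by | 'On or after' removes | 'Post-discontinuation' removes |
|---|---|---|
| Day of stopping (Week 12 visit) | Week 12 value | nothing |
| Last infusion (Week 8 visit) | Week 8 pre-dose value and Week 12 value | Week 12 value |

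The result depends on the undefined date as well as on the word 'on'. Under last-infusion dating, the Week 12 value is lost under either wording.

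**2. The visit-mapping rule.** Suppose an early discontinuation visit falls on Day 60, after a Week 8 visit on Day 56. If its value is retained, SAP 4.1 labels it Week 12 (Day 84), which is 84 - 60 = 24 days early. Day 60 lies in the Week 8 window of 56 ± 7, that is Days 49 to 63.

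**3. The plan's own figure.** Inputs from SAP Section 5: means -1.80 and -0.75, SD 1.25, 40 and 20 participants, two-sided alpha 0.05.

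- Difference = -1.80 - (-0.75) = -1.05.
- SE = 1.25 × sqrt(1/40 + 1/20) = 0.34.
- Power = 85.5% (noncentral t, 58 df) or 86.6% (normal approximation). The stated figure of more than 80% reproduces and is not in dispute.

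**4. Effect of dropping the value from the day of stopping.** 3000 simulated trials per setting used the Week 12 means, SD and arm sizes above, with visits at Weeks 2, 4, 8 and 12. The following are assumed, not taken from the documents:

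- mean changes of -0.6, -1.0, -1.5, -1.8 on 700 mg and -0.3, -0.45, -0.65, -0.75 on placebo;
- constant SD, and correlation 0.5 or 0.7 between visits;
- probability of stopping after the assessment at a visit = 1/(1 + exp(-2(Y - c))), where Y is that visit's change and c = 2.5, 1.5 or 1.0, with stopping possible up to Week 8 or up to Week 12.

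Estimation was by sequential regressions for monotone missing data. This approximates the planned MMRM without its baseline and stratum terms.

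| Discontinuing, 700 mg / placebo | Value kept | Value dropped | Shrinkage |
|---|---|---|---|
| about 4% / 7-9% | -1.05 | -1.01 to -1.03 | 0.02 to 0.04 |
| about 14-15% / 23-28% | -1.05 to -1.06 | -0.95 to -0.99 | 0.06 to 0.11 |
| about 23-26% / 35-42% | -1.05 to -1.06 | -0.90 to -0.96 | 0.09 to 0.16 |
| about 14% / 14%, unrelated to response (correlation 0.6) | -1.05 | -1.05 | none |

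Shrinkage is the difference between kept and dropped within each setting. It arises because the placebo mean moves further than the 700 mg mean. In the second row placebo goes from about -0.75 to between -0.93 and -1.00, and 700 mg from -1.80 to between -1.92 and -1.96.

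A second stopping model gave a consistent answer. In it, 15% to 30% of participants with no improvement at Week 4, 8 or 12 stop that day, so 6% to 11% stop on LY3462817 and 13% to 23% on placebo. Keeping the value gave about -1.05. Dropping it gave -0.98 to -1.03, a shrinkage of 0.02 to 0.07, with about one further placebo Week 12 value lost out of 20.

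**5. Size against precision.** 0.02/0.34 = 0.06 and 0.11/0.34 = 0.32, so at low to moderate discontinuation the shift is about 0.06 to 0.3 standard errors.

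**6. Bound on the loss of information.** If every discontinued participant contributed nothing at Week 12, power would be 83.6%, 81.5%, 79.2% and 76.6% at 5%, 10%, 15% and 20% lost per arm. The rule costs only part of this, because most of those participants would lack a Week 12 value anyway.

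**The case against.** The best defence is that SAP 4.3.2 matches the protocol: excluding data on or after an event is the complement of "MMRM model under MAR is applied to the data prior to treatment discontinuation". That is fair for the estimator cell, but the cell beside it says "No, only use data up until discontinuation", so the protocol does not settle the matter.

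It can also be argued that 'the treatment discontinuation' means the event, not its date. A pre-dose value would then precede the event and survive. The narrower sentences in SAP 4.3.2 and Section 3, and the window in SAP 4.1, support keeping it. However, the word 'on' makes sense only for a date, so this reading leaves the sentence without a clear meaning.

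Three stronger inferences are tempting, and the documents do not support them.

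- *That the lost values are mostly poor ones, chiefly placebo failures.* Protocol 7.1.2 lists participant or investigator decision, pregnancy, malignancy, infection, C-SSRS answers and liver tests, with no lack-of-efficacy criterion. hsCRP results are withheld from sites (Appendix 2), so the DAS28-CRP score itself cannot prompt stopping that day, though its clinical components could. Protocol 4.2 and 7.2 do allow stopping for disease activity, but Section 7.2 expects discontinuation to be uncommon.
- *That the planned end of infusions at Week 14 would erase Week 12 values.* This needs discontinuation to be dated by the last infusion and a designed stop, after the primary endpoint, to count as early discontinuation. No text supports that, although no text rules it out.
- *That SAP 4.1 and 4.3.2 give opposite orders for the same record.* The mapping sentence is a general rule and does not say that mapped values enter the primary MMRM. A given value is either excluded or mapped and used, so the two problems cannot both affect it.

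**Conclusion.** The point holds as an inconsistency with a small, conditional consequence. The SAP gives two exclusion wordings for the primary model, the protocol's estimand row supports either, and the date on which they turn is undefined. Read literally, the most specific sentence removes on-treatment values, possibly including the Week 12 endpoint.

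If stopping is driven by what is seen at that visit, the 700 mg effect shrinks by roughly 0.02 to 0.11 at low to moderate discontinuation. The larger shifts of up to 0.16 need 35% to 42% discontinuation on placebo, which is hard to square with discontinuation being uncommon. If stopping is unrelated to response, the estimate is unbiased and only a little data is lost. These sizes rest on the assumed earlier-visit means, correlations and stopping models. The sample-size calculation is unaffected.

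**What to change.** - In SAP 4.3.2 change 'on or after' to 'after', so that assessments made on or before the date of permanent discontinuation, and before any restricted medication, are kept.
- Define that date. The word change alone is not enough, since last-infusion dating would still remove the Week 12 value in the example. The documents do not describe a field for the decision date, so confirm that the CRF records one.
- State that the planned stop of infusions at Week 14 is not a discontinuation for the Week 12 analysis.
- Use the same wording in SAP Sections 3, 4.1 and 4.3.2, and for the continuous secondary endpoints in 4.4.1.2.3 to 4.4.1.2.7, which take their model from 4.3.2.
- For the MMRM, assign a retained early discontinuation value to the visit whose window contains its actual study day, with the scheduled visit's value taking precedence if both exist. The schedule's ± 7-day tolerances leave Days 36 to 48 and 64 to 76 in no window and put Day 21 in two, so the SAP needs analysis windows that cover these days or a stated rule for them.

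The cost is a few sentences in the SAP and, provided the date is already captured, no new data. The downside is that a few slightly off-schedule values enter the model.
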